## **5.4 Treatment blinding**

### **5.4.1 PK Run-in Part**

Treatment blinding in the PK Run-in Part is not applicable since the part is a single cohort.

### **5.4.2 Parts A and B**

Treatment will not be blinded to patients and investigators since dose frequency and dosages for KAF156 and LUM-SDF may change from cohort to cohort and double-blinding will require triple dummies for 3 different drugs (KAF156, LUM-SDF, and Coartem®). Double-blinding is further complicated by the food requirement where patients assigned to KAF156 and LUM-SDF combinations are required to be fasted while patients assigned to Coartem® are

required to be fed. KAF156, LUM-SDF, and Coartem® will be provided to investigators who will dispense the correct dosage to patients based on IRT's instruction. However, since the primary and secondary objectives of the trial are mainly based on objective, laboratory assessments, this should not bias the efficacy and the safety endpoint assessments. Moreover, the lab technician performing these efficacy assessments will not have knowledge of the treatment arms to which the patients are assigned.

In order to minimize the potential impact of treatment knowledge, treatment allocation, dose information, electrocardiogram (ECG), and PK assessment schedule and concentration data, as well as other data that may result in systematic unblinding will not be uploaded into any Novartis analysis or data review system that is available to the Clinical Trial Team (particularly clinicians, statisticians, programmers) until the database is locked for each part. Further details on data handling are documented in the appropriate data handling plan (DHP)/data management plan (DMP). The pharmacokineticist will be unblinded for PK/drug exposure data only for the whole duration of the study (i.e., Part A and Part B).

During the conduct of Part A and during Part B, summaries of results by treatment arm will be prepared only for Data Monitoring Committee (DMC) assessments. The DMC reports will be performed by an independent team (see [Section 9.7](#)).

The bioanalyst will request a copy of the randomization to facilitate analysis of the samples. The bioanalyst will provide the sample data to the team under blinded conditions. The bioanalyst will keep this information confidential until the final clinical database lock for each part.

## **5.5 Transition from PK Run-in Part to Part A and from Part A to Part B**

Following the PK results from the PK Run-in cohort, the sponsor will set up IRT/dosing of KAF156 for Part A as specified in [Table 3-1](#) and [Appendix 5](#). All investigators will be informed accordingly.

After completion of Part A, the database will be cleaned and locked for Part A. Interim assessment of selected efficacy and safety endpoints will be performed to determine the most effective and safe dose of KAF156 and LUM-SDF combination for each tested dosing regimen and assess the dosage to be used in children in Part B for the selected dosing regimen. The results from Part A and the doses to be used for Part B will be communicated to relevant internal and external stakeholders.

## **5.6 Treating the patient**

Sponsor qualified medical personnel will be readily available to advise on trial related medical questions or problems.

### **5.6.1 Patient numbering**

Each patient is uniquely identified by a Subject Number which is composed by the site number assigned by Novartis and a sequential number assigned by the investigator. Once assigned to a patient, the Subject Number will not be reused.

Upon signing the pre-screening informed consent form, the patient is assigned the next sequential number by the investigator. The investigator or his/her staff will contact the IRT and provide the requested identifying information for the patient to register them into the IRT. The site must select the case report/record form (CRF) book with a matching Subject Number from the electronic data capture (EDC) system to enter data.

If the patient fails to be treated for any reason, the IRT must be notified within 2 days that the patient was not treated. The reason for not being treated will be entered on the Screening epoch Study Disposition CRF.

### **5.6.2 Dispensing the study drug**

Each study site will be supplied with study drugs in individual packaging for each patient.

The study drug packaging has a 2-part label. A unique medication number is printed on each part of this label which corresponds to one of the treatment drugs and dose. Investigator staff will identify the study drug package(s) to dispense to the patient by contacting the IRT and obtaining the medication number(s). Immediately before dispensing the package to the patient, investigator staff will detach the outer part of the label from the packaging and affix it to the source document (Drug Label Form) for that patient's unique subject number.

If a patient vomits study drugs within 1 hour of intake a replacement dose will be given to the patient and the investigator or designee will notify IRT.

Medication number and quantity of treatment drug taken by patients have to be collected by the investigator or designee.

### **5.6.3 Handling of study treatment**

Study treatment must be received by a designated person at the study site, handled and stored safely and properly, and kept in a secured location to which only the investigator and designees have access. Upon receipt, all study treatment must be stored according to the instructions specified on the labels. Clinical supplies are to be dispensed only in accordance with the protocol. Technical complaints are to be reported to the respective Novartis country pharma organization (CPO) Quality Assurance.

Medication labels will be in the locally accepted language and comply with the legal requirements of each country. They will include storage conditions for the study treatment but no information about the patient except for the medication pack number.

The investigator must maintain an accurate record of the dispensing of study treatment in a drug accountability log. The study treatment will be administered to patients under hospital supervision. Monitoring of drug accountability will be performed by monitors during site visits or remotely and at the completion of the trial.

At the conclusion of the study, and as appropriate during the course of the study, the investigator will return all unused study treatment, packaging, drug labels, and a copy of the completed drug accountability log to the Study monitor or to the Novartis address provided in the investigator folder at each site.

#### 5.6.4 Instructions for prescribing and taking study treatment

##### KAF156 and LUM-SDF

Patients must be fasted 3 hours before and 4 hours after KAF156/LUM-SDF administration. Water can be provided ad-libitum. In Part B, pediatric patients may be given non-fatty liquids such as orange juices prior to 1 hour of dosing and 1 hour after dosing and recorded. Patients may receive some food at the time they arrive at the hospital and then be fasted for 3 hours minimum before they receive KAF156/LUM-SDF.

Administration of LUM-SDF and KAF156 must be under staff supervision. Patients will take the KAF156 and LUM-SDF according to the assigned dose level and dosing regimen (once daily for either 1, 2 or 3 days) of the KAF156 and LUM-SDF combination.

The content of LUM-SDF sachet(s) should be emptied in mouth directly and then patients should drink some water. This will ensure that the complete dose is administered without any loss. A pair of scissors is needed to open the LUM-SDF sachets. Subsequently (preferably in 2 min, but in any case < 15 min), KAF156 will be administered orally. Tablet(s) to be swallowed with water.

For the pediatric population in Part B specific strength of the KAF156 tablet and LUM-SDF sachet will be available. These children will be given LUM-SDF as dispersible powder in mouth directly and then patients should drink some water. Subsequently (preferably in 2 min, but in any case < 15 min), KAF156 will be given as film-coated tablets that could be dissolved in pre-specified amount of liquid. Administration of LUM-SDF and KAF156 must be under study staff supervision.

Each patient's mouth must be checked to ensure that the medications were swallowed. In the case that the patient vomits within 1 hour of intake a replacement dose will be given to the patient and the investigator or designee will notify IRT. If the second dose is vomited the patient has to be given non-lumefantrine standard of care.

Food intake information will be collected only on dosing day, i.e., time of last food intake before dosing, time of first food intake after dosing, amount of meal consumed (%) and type of food based on the following 6 categories:

1. none (=no meal)
2. liquid only (zero fat)
3. minimal meal (estimate of < 200 calories, ~ 1 g of fat)
4. light meal (estimate of 200-300 calories, 5-10 g of fat)
5. Standard meal (estimate of 400-500 calories, 20-30 g of fat)
6. high fat meal (estimate of 800-1000 calories, > 50 g of fat)

In Part B, a low fat vehicle may be used for drug administration in children < 6 years old if they are unable to take the medication normally with water, depending on the outcome of Part A.

##### **Coartem®**

With respect to Coartem®, patients will be dosed BID for 3 days (at the following time points: 0, 8, 24, 36, 48, and 60 hours) and must receive a standard meal less than 30 min prior to dosing, as per label. Dosages will be administered according to weight group as described in [Table 5-3](#).

Conventional 20/120 mg and 80/480 mg tablets are to be taken orally with a glass of water. The dispersible tablet is to be dissolved in 10 mL of water in a small cup, and subsequently administered orally under hospital supervision; thereafter the cup will be rinsed with an additional 10 mL of water and the content is to be swallowed again. This procedure will be repeated as necessary in order to administer the amount of doses indicated.

Coartem® medication should be followed whenever possible by food/drink (mother's milk, broth, sweetened condensed milk, etc.) as appropriate.

All kits of study treatment assigned by the IRT will be recorded in the IRT and IMP accountability log.

Food intake information will be collected on each dosing day, i.e., time of last food intake before dosing, time of first food intake after dosing, amount of meal consumed (%) and type of food based on the following 6 categories:

1. none (=no meal)
2. liquid only (zero fat)
3. minimal meal (estimate of < 200 calories, ~ 1 g of fat)
4. light meal (estimate of 200-300 calories, 5-10 g of fat)
5. Standard meal (estimate of 400-500 calories, 20-30 g of fat)
6. high fat meal (estimate of 800-1000 calories, > 50 g of fat)

### **5.6.5 Permitted dose adjustments and interruptions of study treatment**

No dose adjustments other than according to body weight group as described above (see [Section 5.1.1](#)) are permitted.

Additional doses can be given in case of vomiting (see [Section 5.6.4](#)).

The changes must be recorded on the electronic Dosage Administration Record (eCRF).

For both Parts A and B, patients who vomit within 1 hour of trial drug administration will be given a replacement dose, and IRT must be notified.

For the PK Run-in Part, patients who vomit within 1 hour of trial drug administration will not be assessed in the PK analysis. In such case, additional patients will be dosed to compensate for the missing PK data and to achieve the total number of 12 patients with evaluable PK data in the PK Run-in Part.

### **5.6.6 Rescue medication**

The following circumstances warrant discontinuation of study treatment and the implementation of rescue medication (see [Section 6.5.8](#)):

#### **Early Treatment Failure (ETF)**

- Development of danger signs or severe malaria on Day 2, Day 3, Day 4 in the presence of parasitaemia.
- Parasitaemia on Day 3 higher than Day 1 count irrespective of axillary temperature
- Parasitaemia on Day 4 with axillary temperature  $\geq 37.5^{\circ}\text{C}$

- Parasitaemia on Day 4 equals to or more than 25% of count on Day 1

#### **Late Clinical Failure (LCF)**

- Development of danger signs or severe malaria on any day from Day 5 to Day 43 in the presence of parasitaemia without previously meeting any of the criteria of early treatment failure
- Presence of parasitaemia and axillary temperature  $\geq 37.5^{\circ}\text{C}$  on any day from Day 5 to Day 43 without previously meeting any of the criteria of Early Treatment Failure

#### **Late Parasitological Failure (LPF)**

- Presence of parasitaemia on any day from Day 8 to Day 43 and axillary temperature  $< 37.5^{\circ}\text{C}$  without previously meeting any of the criteria of Early Treatment Failure or Late Clinical Failure

Commencement of rescue medication with a combination antimalarial product (local standard at the discretion of the investigator or a medically qualified person) may occur after start of trial medications and up to 43 days after the last dose of KAF156/LUM-SDF as deemed necessary by the investigator. Lumefantrine-based treatment must be avoided in case of early treatment failure (ETF). Patients will be monitored, either in clinic, by telephone, or via home visits for three days to ensure adherence to the rescue medication therapy. These patients will not be replaced and will not discontinue the study (i.e., all the examinations as per the assessment schedule and all CRF pages for this patient will need to be completed).

Safety blood tests (Full Blood Count (FBC) and Blood chemistry) will be collected on the initial day of rescue medication dosing. Blood films and blood sampling for parasite count and genotyping must be taken before giving the established anti-malarial treatment.

Patients treated with at least one dose of trial medications will continue to be followed-up until Day 43 according to schedule.

Use of rescue medication (including exact rescue regimen and route of administration) must be recorded on the Concomitant medications/Significant non-drug therapies after start of study drug.

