**Table 3-2 Cohort Success Criteria**

Efficacy	The lower limit of 2-sided 95% exact confidence interval for PCR corrected ACPR at Day 29 is greater than 80%
Safety	A comprehensive assessment of AEs, SAEs, lab data and ECG for investigational and reference product (Coartem ® ) by DMC/Novartis will determine the tolerability success criteria for the cohorts

If needed, secondary efficacy parameters can also be evaluated to discriminate between cohorts in Part A.

Selected cohorts that pass the efficacy/safety hurdles will be further evaluated in Part B.

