## 5.7 Study completion and discontinuation

### 5.7.1 Study completion and post-study treatment

Each patient will be required to complete the study in its entirety and thereafter no further study treatment will be made available to them.

A patient will be considered to have completed the study when the patient has completed the last visit planned in the protocol, and any repeat assessments associated with this visit have been documented and followed-up appropriately by the investigator.

Patients who discontinue study drug and are put on rescue medication will be followed for the entire study duration (i.e., until Day 43).

The investigator and/or referring physician must provide follow-up medical care for all patients who are prematurely withdrawn from the study, or must refer them for appropriate ongoing care. This care may include:

- Treatment of their malaria and complications
- Treatment of secondary infections
- Treatment of associated diseases

An independent Data Monitoring Committee (DMC) will review patient safety at several time points (see [Section 8.4](#)) and may recommend stopping a cohort or the study early for safety reasons.

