2.2 Analysis sets

Randomized set

All patients who are enrolled in the PK run-in cohort or randomized in Parts A and B. Unless otherwise specified, misrandomized patients will be excluded from the randomized set. For the PK run-in part, this set includes all patients with informed consent and treated with study medication.

Misrandomized patients, if identified from IRT, include patients who are screen-failures, but have been randomized by the investigator before eligibility was finally assessed or mistakenly, and have not been treated. If patients were re-screened and successfully randomized, they will be included in the randomized set according to the treatment assigned in the last randomization.

Note: There is no randomization in the PK run-in cohort. For this cohort, the more appropriate terminology is “Enrolled set”. However, ‘Randomized set’ is used for simplicity.

Full analysis set (FAS)

FAS will be comprised of all patients from Randomized set who take at least one dose of study treatment during the treatment period and whose baseline *P. Falciparum* asexual parasitemia count is greater than 0. Following the intent-to-treat principle, patients will be analyzed according to the treatment group assigned to at randomization.

Safety set (SAF)

Safety set includes all patients who take at least one dose of study drug during the treatment period. Patients will be analyzed according to treatment received. In particular, patient will be

analyzed in the same treatment group as randomized if s/he receives at least one dose of the study medication of that group.

Per-protocol set (PPS)

Per-protocol set will be comprised of patients in FAS who

- did not have any important protocol deviations
- took at least 80% of randomized study medication(s). If a patient vomited the original dose but did not vomit the replacement dose, the patient is considered as taking the dose of study medication. Since a partial compliance, such as 83%, etc., can be calculated based on the actual dosage taken (see Section 2.4.1), this allows patients assigned to KAF156 and LUM-SDF arms to take partial dosages which slightly deviates from the protocol.
- did not take non-study drug antimalarial medications prior to Day 29 unless experiencing any treatment failure (ETF, LCF, LPF) (e.g new infections between Day 8 and Day 29), and

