2.7.2.3 Parasite clearance time (PCT) and fever clearance time (FCT)

Descriptive statistics (mean, standard error, median, quartiles) will be presented using the Kaplan-Meier method. Kaplan-Meier curves will be provided.

PCT will be calculated based on uncorrected asexual parasite counts. Patients without parasite clearance for whatever reason will be censored at the time of last parasite assessment. Patients who were enrolled on the basis of history of fever and did not subsequently have a fever at pre-dose will not be included in the analysis of FCT. Patients without fever clearance for whatever reason will be censored at the time of last temperature assessment. Patients who received any antimalarial medication (including rescue medication) before (parasite or fever) clearance will be censored at the first use of antimalarial medication. The difference between each test group and control will be evaluated using a log-rank test. Patients who did not experience a clearance will be censored at the time of last relevant assessment (parasite or fever). For the pooled analysis, the log-rank test will be stratified by Part.

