2.8.1 Adverse events (AEs)

The number and percent of patients with treatment emergent adverse events will be presented. The treatment emergent adverse events (events started on or after the first dose of study medication or events present prior to the first dose of study medication but increased in severity based on preferred term) will be summarized by primary System Organ Class (SOC) and Preferred Term (PT).

Adverse events will be summarized by presenting, for each treatment group, the number and percentage of patients having at least one AE, having an AE in each primary system organ class and having each individual AE (preferred term). Summaries will also be presented for AEs by severity (Toxicity grade) and for study treatment related AEs. If a patient reported more than one adverse event with the same preferred term, the adverse event with the greatest severity will be presented. If a patient reported more than one adverse event within the same primary system organ class, the patient will be counted only once with the greatest severity at the system organ class level, where applicable.

The MedDRA version used for reporting the adverse events will be described in a footnote.

The most common adverse events reported ($\geq z$ % in any group for each preferred term in the table by SOC and PT) will be presented in the clinical study report by descending frequency according to its incidence in overall group starting from the most common event. Here threshold value z is set to 5 (%) but it may be updated following review of the dry run outputs.

Separate summaries will be provided for deaths, serious adverse events, severe malaria, other significant adverse events leading to treatment discontinuation and adverse events leading to dose adjustment.

Serious adverse events in screening phase will be flagged in data listing due to rare frequency.

Patients who experienced a grade 3 or grade 4 AE will be summarized.

For the legal requirements of ClinicalTrials.gov and EudraCT, two required tables on treatment emergent adverse events which are not serious adverse events with an incidence greater than 5% and on treatment emergent serious adverse events and SAE suspected to be related to study treatment will be provided by system organ class and preferred term on the safety set.

If for a same patient, several consecutive AEs (irrespective of study treatment causality, seriousness and severity) occurred with the same SOC and PT:

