2.8.3 Other safety data

2.8.3.1 ECG and cardiac imaging data

The following quantitative variables will be summarized for averaged triplicate ECG: heart rate, RR interval, PR interval, QRS interval, QT interval, QTcB (QT interval corrected for heart rate according to Bazett) and QTcF (QT interval corrected for heart rate according to Fredericia).

Descriptive summary statistics for the change from baseline for each post-baseline visit will be performed by ECG parameters and treatment group.

Patients with notably high QT, HR and fever ($\geq 37.5^\circ\text{C}$ for *axillary* or $\geq 38.3^\circ\text{C}$ for other routes) will be provided.

To assess the temporal correlations mean change of QTcF over time, mean change of ECG HR over time, mean change of temperature over time, and PK concentration of KAF156 and lumefantrine over time will be plotted with all panels aligned on the x-axis (Time after dosing).

QTc will be summarized categorically by computing the number and percentage of patients at each time point and at the maximum post baseline value with following:

- QT, QTcF, or QTcB
 - > 450 and ≤ 480 ms
 - > 480 and ≤ 500 ms
 - > 500 ms
 - Increase from Baseline of ≥ 30 ms to < 60 ms
 - Increase from Baseline of ≥ 60 ms
- HR for age ≥ 18 years
 - Increase from baseline $>25\%$ and to a value > 100 bpm
 - Decrease from baseline $>25\%$ and to a value < 50 bpm
- HR for age < 18 years
 - $>$ upper limit of normal (ULN) defined in Table 2-3
 - $<$ lower limit of normal (LLN) defined in Table 2-3
- PR

- Increase from baseline >25% and to a value > 200 ms
- New value of > 200 ms
- QRS
 - Increase from baseline >25% and to a value > 120 ms
 - > 120 ms

Table 2-3 Normal heart rates (resting) by age

Age (years)	Normal range bpm
1 - ≤ 3	70 - 110
3 - ≤ 6	65 -110
6 - ≤12	60 -95
>12	55 -85

Source: Nelson Textbook of Pediatrics, 18th Edition

A line plot by patient (Spaghetti plot) will be provided by visit and treatment group.

In addition, shift tables comparing baseline ECG results (normal, abnormal, not available, total) with the post-baseline results will be provided by visit and at the worst post-baseline result (normal, abnormal, not available, total).

A listing of all newly occurring or worsening abnormalities as compared with baseline will be provided, as well as a by-patient listing of all quantitative ECG parameters.

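### SAP 2.8 does not separate safety data before and after rescue, so arms with more rescue can look less tolerable in the all-causality AE, notable-laboratory and maximum-QTc outputs

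*Protocol*

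**What the plan says.** **Follow-up.** Protocol 5.6.6 gives rescue as a local-standard combination antimalarial. Of rescued patients it says "These patients will not be replaced and will not discontinue the study", and "Patients treated with at least one dose of trial medications will continue to be followed-up until Day 43 according to schedule". Full blood count and blood chemistry are also taken on the first day of rescue.

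**Grouping.** Under SAP 2.2 (safety set) a patient is "analyzed in the same treatment group as randomized if s/he receives at least one dose of the study medication of that group".

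**Safety summaries.** SAP 2.8.1 defines treatment-emergent events as "events started on or after the first dose of study medication", plus earlier events that worsen, and gives no end point. SAP 2.8.2 summarises all laboratory tests performed, tabulates the liver criteria of Table 2-2 and lists the renal criteria. SAP 2.8.3.1 categorises QTc "at each time point and at the maximum post baseline value". Unscheduled values are mapped into visit windows (SAP 5.1.4), and for notable abnormalities the most extreme value in the window counts (Table 5-7).

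**Contrast in efficacy.** For clearance times, SAP 2.7.2.3 says: "Patients who received any antimalarial medication (including rescue medication) before (parasite or fever) clearance will be censored".

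**Use.** The safety criterion in Protocol Table 3-2 is "A comprehensive assessment of AEs, SAEs, lab data and ECG for investigational and reference product". SAP Table 2-8 sends AE, laboratory and ECG outputs to the DMC at the periodic reviews and at the end of Part A.

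**The concern.** A patient rescued on Day 15 still has four weeks of follow-up, after a different antimalarial and during or after a second malaria episode. In the all-causality AE tables, the notable laboratory outputs and the QTc maximum, whatever happens in those weeks is counted under the randomised regimen. Summaries of the form at-least-one-event or worst-value can only rise when data are added, so the direction is known for them.

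Rescue will not be equally common across arms. Protocol 3.3 expects the 1-day doses to be less likely to be effective. Rescue under 5.6.6 is triggered by parasitaemia criteria that do not distinguish recrudescence from new infection. The tolerability comparison of 1-, 2- and 3-day regimens and Coartem therefore partly reflects how much rescue each arm received, and that comparison feeds the choice of cohorts for Part B.

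**Working it through.** **Plan figures that fix the arm size.** Null 80%, exact two-sided 95% interval, 42 per-protocol patients: the lower limit exceeds 80% with at least 39 responders. The exact one-sided type I error is 0.0208 and the power at a true rate of 95% is 0.843, which agrees with the stated power of at least 80%. Randomised numbers: 42/0.84 = 50, 21/0.84 = 25, and 6 × 50 + 25 = 325, as stated.

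**Exposure after rescue.** Follow-up left is 43 minus the rescue day: 35 days from Day 8, 28 from Day 15, 14 from Day 29.

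**Spurious gap in AE incidence.** The documents give no rescue rate, AE rate or named rescue drug, so all inputs are assumptions. Let *b* be the share of patients with an AE before rescue (equal in both arms), *f* the share rescued, and *r* the chance that a rescued patient with no earlier AE has one after rescue. Observed incidence is *b* + (1 − *b*) *f r*, and the gap between two arms is (1 − *b*) *r* (*f*₁ − *f*₂).

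- *b* = 40%, *f* = 40% vs 10%, *r* = 20%: 44.8% vs 41.2%, gap 3.6 points.
- The same with *r* = 50%: 52% vs 43%, gap 9 points.
- *b* = 30–50%, *r* = 20–50%, *f* = 40% vs 10% or 30% vs 5%: smallest gap 0.5 × 0.2 × 0.25 = 2.5 points, largest 0.7 × 0.5 × 0.30 = 10.5 points.
- Milder case, *f* = 20% vs 5%, *b* = 30–70%, *r* = 10–50%: smallest gap 0.3 × 0.1 × 0.15 = 0.45 points, largest 0.7 × 0.5 × 0.15 = 5.25 points. With 50 per arm this is 0.2 to 2.6 patients.
- Rare notable abnormality, *b* = 2%, *f* = 20% vs 5%, *r* = 5–30%: 0.98 × 0.15 × *r* = 0.7 to 4.4 points. At the upper end the arms would read 7.9% vs 3.5%.

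**Limit on QTc.** After the treatment epoch, Table 6-2 schedules ECGs only at Day 8 and Day 43, and SAP Table 5-6 has only two matching windows (Days 6–25; Day 26 and above). A patient rescued after the Day 8 visit normally adds one scheduled post-rescue ECG, plus any unscheduled ones.

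**Interaction with the efficacy criterion.** An arm of 42 that passes has at most 3 PCR-corrected non-responders by Day 29 (3/42 = 7.1%). For 20% of such an arm to be rescued, roughly 20 − 7 = 13 points must come from new infection or from failure after Day 29; for 40%, roughly 33 points.

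**The case against.** Several counter-arguments have force.

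- **Not every later event is credited to the regimen.** A reader might infer that it is. SAP 2.8.1 also tabulates treatment-related AEs and related SAEs, and laboratory and ECG data are also shown by visit; the Day 1–4 visits hold almost no post-rescue data except after early failure. This stands, and it limits the point to the all-causality, notable-value and maximum-value outputs. The related-AE table is only a partial remedy, because causality is judged open-label and does not extend to laboratory or QTc data.
- **The rescue drug is not the only source.** Recurrent malaria contributes too, and illness after a failed regimen is arguably a consequence of that regimen. Counting it is a legitimate treatment-policy view, so the all-follow-up tables should stay. The clearance-time censoring is also an imperfect analogy, since rescue itself produces clearance.
- **Selection is partly protected.** A reader might infer that good short regimens would be rejected. An arm with many recrudescences fails the efficacy criterion first, and the safety criterion is a judgement with no numeric threshold. The DMC also sees concomitant medication, early failures and SAE narratives. This largely stands; the remaining route is rescue for new infection or for failure after Day 29.
- **The size is within noise.** At 40% incidence and 50 per arm, the standard error of a difference is √(2 × 0.4 × 0.6/50) = 9.8 points. That is true, but it describes random error, whereas this is a shift in a known direction.
- **The DMC tables are set out in a separate plan**, so what they contain beyond Table 2-8 cannot be checked here.

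**Conclusion.** The gap is real and confined to SAP 2.8.1, 2.8.2 and 2.8.3.1: no safety output separates data before and after rescue or another non-study antimalarial. Following rescued patients to Day 43 is correct and is not the fault. For at-least-one-event and worst-value summaries, extra rescue can only make an arm look worse; mean laboratory changes could move either way.

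The size is unknown. Under the assumed rates the spurious gap in AE incidence lies between 0.45 and 10.5 points, and the QTc effect is limited by the few scheduled late ECGs. The upper part of the range applies to arms that would pass the efficacy criterion only if most rescue was for new infection or came after Day 29. The documents do not support saying that short regimens will be wrongly dropped. They do support saying that a comparison used for a stated selection criterion mixes regimen effects with rescue effects, and that this can be separated cheaply. The primary efficacy analysis is untouched.

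**What to change.** Keep the planned all-follow-up tables and add, in SAP 2.8.1, 2.8.2 and 2.8.3.1, supportive by-arm tables of AEs and SAEs, notable liver and renal laboratory values, and notable QTc. Limit them to data before the first rescue or other non-study antimalarial dose, identified from Table 5-8.

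- State a rule for the day of rescue. AEs carry dates without times (Protocol 7.1), and 5.6.6 does not say whether the rescue-day safety bloods are drawn before or after the first rescue dose.
- For AEs, give the Kaplan-Meier cumulative incidence of first AE, censored at that dose, or incidence in a fixed early window. The former assumes that rescued patients would otherwise have had the same later AE risk as the rest.
- Do not use a rate per 100 patient-days. If AEs cluster early, it penalises the arm with less time at risk. With 40% vs 10% rescued at Day 22, mean time at risk is 0.6 × 43 + 0.4 × 22 = 34.6 vs 0.9 × 43 + 0.1 × 22 = 40.9 days. The same 40% pre-rescue incidence then gives a rate 40.9/34.6 = 1.18 times as high, with no true difference.
- Show the number rescued and the time at risk by arm, and flag later records in the listings.
- Give both sets to the end-of-Part-A assessment and the DMC.

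Cost: a second set of the main safety tables and matching DMC shell wording. No new data are needed, since rescue use is already recorded and first antimalarial use is already required for SAP 2.7.2.3. The pre-rescue set omits late toxicity of the randomised regimen in rescued patients, so it supplements the full tables and does not replace them.
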